### **3.3.2 Pre-Cycle before Subsequent Cycles (Day -3 to Day 1)**

- Physical exam, query for visual symptoms
- Performance status (ECOG)
- Weight (can be obtained on Day -4 to Day 1) - do not change dose during a cycle; dose should be adjusted for weight change  $\geq$  10% from screening in subsequent cycles.

- AEs and concurrent medications
- [REDACTED]
- [REDACTED]
- Uric acid, creatine kinase (CK or creatinine phosphokinase), GGT, PT, Haptoglobin
- 12-lead ECG analyzed by central vendor, ERT.

### 3.3.3 During Cycle

- Day 1 (Prior to dosing)
  - Patients should be asked about visual symptoms and reminded to report any visual symptoms during the cycle. New visual symptoms of Grade 2 or greater should be evaluated with a full ophthalmologic assessment.
  - [REDACTED]
- Days 1, 3, and 5
  - AEs and concurrent medications
  - CBC with differential and peripheral blood smear
  - Chem7 ( sodium, potassium, chloride, bicarbonate, glucose, BUN, creatinine)
  - mineral panel (calcium, magnesium, phosphorus, albumin)
  - hepatic panel (AST-SGPT, ALT-SGOT, total bilirubin, direct bilirubin, alkaline phosphatase )
  - LDH
  - Urinalysis (Day 1 only)
  - Vital signs including pulse oximetry
  - Physical exam, query for visual symptoms
  - Orthostatic BP
  - Moxetumomab pasudotox dosing
- Days 1 and 5
  - 12-lead ECG (analyzed by central vendor, ERT), 30-60 minutes post end of infusion (Cycle 1 only)
  - PK (EDTA)
    - Day 1 pre (Odd cycles and Cycle 2)
    - Day 1 immediately post (Odd cycles and Cycle 2)
    - Day 1, 3 hours post (Cycles 1 and 2)
    - Day 5 pre, immediately post, 1 hour, 3 hours, 6 hours post (Cycle 1 only)
- Day 8 (±1 day): CBC with differential and peripheral blood smear , Chem7, mineral panel, hepatic panel, LDH, vital signs, orthostatic BP, weight, AEs, concurrent medications [REDACTED]

- Recommended on Days 15 and 21 (each  $\pm 2$  days): CBC with differential and peripheral blood smear, Chem 7 (sodium, potassium, chloride, bicarbonate, glucose, BUN, creatinine), mineral panel (calcium, magnesium, phosphorus, albumin), hepatic panel (AST-SGPT, ALT-SGOT, total bilirubin, direct bilirubin, alkaline phosphatase), LDH, AEs, concurrent medications and vital signs
- [REDACTED] IgA, IgG, IgM, C3, C4, and CH50 should be repeated upon both diagnosis and resolution of HUS and  $>$  Grade 2 CLS. Measurement of tumor burden is also recommended, but not required, in the event of HUS

### Interim Disease Assessment (Optional)

- During treatment and prior to completion of 6 cycles of therapy, if blood counts are consistent with CR for at least 4 weeks, an interim disease assessment may be performed at the discretion of the investigator. All assessments listed in Section 3.3.4.1 are required if an optional interim disease assessment is performed. Imaging (CT or MRI) and ophthalmologic examination may be deferred for up to 7 days until after the bone marrow aspirate and biopsy if CR without MRD is confirmed. For a response less than CR without MRD, therapy should resume and imaging and ophthalmologic examination may be deferred (if not performed concurrently with the bone marrow examination) until the end of treatment assessment.

### 3.3.4 Tests in Follow-up After Treatment Ends:

#### 3.3.4.1 All patients 28-42 days after the first day of dosing of prior cycle (end of treatment assessment)

- History and physical exam, concurrent medications, AEs, performance status (ECOG)
- Pulse Oximetry with vital signs and weight
- Ophthalmologic exam (slit lamp and fundus)
- 12-lead ECG (analyzed by central vendor, ERT)
- Imaging with CT or MRI for lymphadenopathy and organomegaly
- Bone marrow biopsy and aspirate with flow cytometry/sequencing
- CBC with differential (no peripheral blood smear)
- Chem 7 (sodium, potassium, chloride, bicarbonate, glucose, BUN, creatinine)
- mineral panel (calcium, magnesium, phosphorus, albumin)
- Hepatic panel (AST-SGPT, ALT-SGOT, total bilirubin, direct bilirubin, alkaline phosphatase)
- Uric acid, total protein, triglycerides, cholesterol, GGT
- PT, PTT, LDH, fibrinogen, quantitative immunoglobulins, CK, CRP, serum ferritin

- TSH, fT4, serum amylase, serum lipase, haptoglobin, and urinalysis
- [REDACTED]
- [REDACTED]
- [REDACTED]
- Patients with SD, PR or CR are then followed until relapse from baseline

#### **3.3.4.2 Follow-up for those in Complete Response**

- CBC with differential (no peripheral blood smear) performed monthly until 181 days after documentation of CR/end of treatment assessment, then every 3 months for 2 years, and then every 6 months thereafter

#### **3.3.4.3 For those not in Complete Response**

- CBC with differential (no peripheral blood smear) performed every 3 months for 2 years after end of treatment, then every 6 months thereafter

#### **3.3.4.4 For all patients in follow-up**

The Day 181 post-end of treatment assessment may not be performed prior to Day 181. This assessment may be performed between Day 181 and Day 195 post-end of treatment.

Refer to [Table 10-2](#):

- History and physical exam, concurrent medications, pulse oximetry with vital signs and weight, performance status
- [REDACTED]
- [REDACTED]
- For subjects with CR or PR, disease assessment by CT or MRI at Day 181 and 18-month time points after the end of treatment.
- Bone marrow biopsy and aspirate with flow cytometry/sequencing is required [REDACTED]
- Peripheral blood for disease B-cell clone detection [REDACTED]
- Chem 7/Acute Care Panel (sodium, potassium, chloride, bicarbonate, glucose, BUN, creatinine)
- Mineral panel (calcium, magnesium, phosphorus, albumin)
- Hepatic panel (AST-SGPT, ALT-SGOT, total bilirubin, direct bilirubin, alkaline phosphatase)

- Uric acid, total protein, triglycerides, cholesterol, GGT, PT, PTT, LDH, quantitative immunoglobulins, CK, CRP, serum ferritin, TSH, fT4, serum amylase, serum lipase
- Haptoglobin (end of treatment and Day 181 post-end of treatment only)
- Urinalysis (end of treatment and Day 181 post-end of treatment only)

## 4 REGISTRATION PROCEDURES

Study participation begins (ie, a subject is “enrolled”) once written informed consent is obtained. Once informed consent is obtained, a subject identification (SID) number will be assigned by a central system (eg, an interactive voice response system), and the screening evaluations may begin to assess study eligibility (inclusion/exclusion) criteria. The SID number will be used to identify the subject during the screening process and throughout study participation, if applicable.

A master log of all consented subjects will be maintained at the site and will document all screening failures (ie, subjects who are consented but do not meet study eligibility criteria), including the reason(s) for screening failure. Subjects who fail to meet the inclusion/exclusion criteria and are rescreened will receive a new SID number.

## 5 TREATMENT PLAN

### 5.1 Agent Administration

Treatment may be administered on either an inpatient or outpatient basis. Appropriate dose modifications are described in Section 6. No investigational or commercial agents or therapies other than those described below may be administered with the intent to treat the patient's malignancy. Seventy-seven evaluable patients will be enrolled to receive moxetumomab pasudotox. Unevaluable patients may be replaced as discussed in Section 13.5.

#### 5.1.1 Moxetumomab pasudotox

Moxetumomab pasudotox (40 µg/kg) will be administered by IV infusion over 30 (± 10) minutes on Days 1, 3 and 5 of each 28-day cycle until documentation of CR or for up to 6 cycles, progressive disease (PD), initiation of alternate therapy or unacceptable toxicity. The cycle interval can be decreased by up to 2 days. For a dosing delay, refer to Section 6. Subjects will receive up to 6 cycles of therapy.

In an attempt to prevent renal insufficiency, patients will receive fluid and aspirin prophylaxis. Patients will receive low-dose aspirin orally (81 mg daily or local standard dose)

on Days 1-8 of those cycles with platelet counts  $\geq 100 \times 10^9/L$ . Aspirin will be held on days where the platelet count is below  $75 \times 10^9/L$ . Patients will receive 1 L of 5% dextrose 0.45% NaCl, (recommended over 2-4 hours) prior to the beginning and after the end of each moxetumomab pasudotox infusion. Patients under 50 kg may receive 0.5 L instead of 1 L of fluid before the beginning and after the end of moxetumomab pasudotox infusion. On Days 0-8 of the cycle, patients are expected to drink at least 3 liters of fluid/day.

To mitigate risk for allergic reaction and fever, patients will be premedicated with 10- 25 mg hydroxyzine (dose to be determined by the investigator), 650 mg of acetaminophen, and 150 mg ranitidine orally 30-90 minutes prior to every moxetumomab pasudotox infusion. After the end of infusion, patients are recommended to receive acetaminophen 650 mg orally every 6 hours x 4 doses and hydroxyzine 10-25 mg orally every 8 hours for 2 doses. Substitutions of diphenhydramine for hydroxyzine and famotidine or cimetidine for ranitidine are permitted. In subjects experiencing infusion-related reactions, including, but not limited to pyrexia, nausea, or dyspnea, premedication with dexamethasone 4 mg intravenous (IV) or oral may be administered at the investigator's discretion as secondary prophylaxis.

Moxetumomab pasudotox will be infused in 50 mL of 0.9% NaCl containing IV Bag Protectant over 30 ( $\pm 10$ ) minutes. Vital signs will be obtained every 15 ( $\pm 5$ ) minutes during the infusion, then every hour ( $\pm 30$  minutes) for an additional 4 hours during Cycle 1. During subsequent cycles, vital signs will be obtained every 15 ( $\pm 5$ ) minutes during the infusion, then every hour ( $\pm 30$  minutes) for an additional 2 hours. Vital signs will also be obtained on Day 8  $\pm 1$  day for the first 3 dosing cycles. Patients will be monitored for orthostatic hypotension on Days 1, 3 and 5 of each cycle prior to moxetumomab pasudotox. Medications and equipment will be available at the patient's unit for treatment of an allergic reaction (including epinephrine, oxygen, corticosteroids, diphenhydramine). These procedures will be followed for all cycles of moxetumomab pasudotox.

Additional recommended safety monitoring includes weekly serum creatinine/albumin monitoring on Days 8, 15 and 21 ( $\pm 1$  day) of Cycle 1 with additional attention to fluid status and weight. Investigator should consider establishing a maximum fluid intake of 6000 mL/day during the first cycle of drug administration with consideration of diuresis with a 5-10% increase in weight above baseline. The investigator may elect to have subjects measure their weight daily with further evaluation indicated if weight gain ( $> 5\%$ ) is noted.

Subjects with hyperuricemia of  $> 10$  mg/dL ( $> 0.59$  mmol/L) prior to administration of moxetumomab pasudotox will receive allopurinol 300 mg once daily for tumor lysis

syndrome (TLS) prophylaxis. Treatment of TLS will be based on institutional guidelines. Adequate *Pneumocystis carinii* pneumonia (PCP) prophylaxis will be provided for patients receiving corticosteroids  $\geq 10$  mg of prednisone daily or equivalent, CD4 lymphocyte count  $< 0.2 \times 10^9/L$ , or at the discretion of the investigator. Viral prophylaxis is also required for subjects receiving chronic corticosteroids or with lymphopenia.

Patients should not receive non-steroidal anti-inflammatory medications (NSAIDs), other than aspirin for prophylaxis of renal insufficiency, during the course of the study through 7 days after the last dose of moxetumomab pasudotox.

An event of  $\geq$  Grade 2 hypercalcemia with calcium level corrected for serum albumin will require a delay in dosing until resolution to  $<$  Grade 2.

If visual symptoms  $\geq$  Grade 2 are reported, an ophthalmologic examination including slit-lamp and fundoscopic evaluation is required.

If a  $\geq 10\%$  increase in body weight due to fluid overload occurs, it is recommended that imaging of the chest is obtained for any evidence of pulmonary edema so appropriate treatment may be instituted promptly.

### 5.1.2 Reporting Product Complaints

Any defects with the investigational product must be reported *immediately* to the MedImmune Product Complaint Department by the site with further notification to the site monitor. All defects will be communicated to MedImmune and investigated further with the Product Complaint Department. During the investigation of the product complaint, all investigational product must be stored at labeled conditions unless otherwise instructed.

Product defects may be related to component, product, or packaging and labeling issues. The list below includes, but is not limited to, descriptions of product complaints that should be reported.

- **Component Issue:** Defect in container or dosing mechanism of the investigational product. The component defect may be damaged, missing, or broken. Component examples include vials, stoppers, caps, spray barrels, spray nozzles, or plungers.
- **Product Issue:** Defect in the product itself. The product appearance has visual imperfections such as foreign particles, crystallization, discoloration, turbidity, insufficient volume, or anything that does not apply to the product description.
- **Packaging/Labeling Issue:** Defect in the packaging or labeling of the product. The packaging or labeling defects may be damaged or unreadable, or the label may be missing.

When reporting a product complaint, site staff must be prepared to provide the following information:

1. Customer information: reporter name, address, contact number, and date of complaint.
2. Product information: product name, packaging kit number or lot number, expiry date, and clinical protocol number.
3. Complaint information: complaint issue category and description.

MedImmune contact information for reporting product complaints:

[REDACTED]

[REDACTED]  
[REDACTED]

[REDACTED]

[REDACTED]  
[REDACTED]  
[REDACTED]  
[REDACTED]

## **5.2 General Concomitant Medication and Supportive Care Guidelines**

### **5.2.1 Concomitant Medications**

Subjects may receive medications as supportive care or to treat AEs as deemed necessary by the investigator or the subject's physician.

All concomitant medications given to the subject from the time the subject signs the informed consent form through 181 days after end of treatment of moxetumomab pasudotox will be recorded on the source document. Beyond 181 days after the end of treatment of moxetumomab pasudotox until end of study, only administrations of blood component transfusions and hematopoietic growth factors will be recorded.

Subjects should continue to take their usual chronic maintenance medications (such as antihypertensives, thyroid replacement therapy, vitamin or mineral supplements) during the course of the study other than those contraindicated by the inclusion/exclusion criteria.

Instructions for specific medications are listed below:

1. Prophylactic use of hematopoietic growth factors, such as filgrastim, sargramostim, or pegfilgrastim, is permitted when IV antibiotics are given for fever ( $> 38.0^{\circ}\text{C}$ ) and neutropenia ( $< 0.5 \times 10^9/\text{L}$ ). Use at the discretion of the study principal investigator (PI) for Grade 4 neutropenia without fever is permitted but discouraged.
2. Concurrent chemotherapy, radiotherapy, immunotherapy, biologic, and hormonal therapy for treatment of cancer during the study are not permitted.
3. Use of steroids is not routinely recommended to prevent CLS or fever from moxetumomab pasudotox; however, secondary prophylaxis for infusion-related reactions with dexamethasone 4 mg IV or oral may be administered at the investigator's discretion.
4. Use of NSAIDs is not permitted from the first dose of the cycle through 7 days after the last dose of the cycle.

## **5.2.2 Supportive Care**

### **5.2.2.1 Infections/Fever and Neutropenia**

Fever [REDACTED] may be treated symptomatically.

### **5.2.2.2 Blood Product Support**

Symptomatic anemia should be treated with appropriate red blood cell (RBC) support. Transfusion is generally recommended if the hemoglobin falls below 8g/dL, but lower levels are acceptable particularly for younger patients. Platelets are generally given when the platelet count is  $< 10 \times 10^9/\text{L}$  or when there is bleeding.

### **5.2.2.3 Cytokine Support**

Prophylactic filgrastim (G-CSF) or sargramostim (GM-CSF) is not indicated for chemotherapy in HCL but may be used in special situations, for example, when patients have serious neutropenic infections.

### **5.2.2.4 Capillary Leak Syndrome**

Any subject with any Grade 2 weight gain, albumin, hypotension, edema, hypoxia, or pulmonary AEs will be evaluated by thorough clinical examination including vital signs and pulse oximetry, assessment of albumin, CBC, electrolytes, BUN, and creatinine. A chest x-ray will be obtained if clinically indicated. These subjects will be prospectively monitored for the potential worsening of the above symptoms. Subjects who develop CLS will be managed according to the respective institutional standards. It is important to recognize that weight gain during CLS is often associated with intravascular volume depletion rather than overload. Thus, use of diuretics should be avoided unless patients are experiencing AEs related to weight gain, particularly when associated with dyspnea. Albumin infusions may be used to permit diuresis with or without diuretics by transiently raising oncotic pressure, but

the need for albumin infusions is generally limited to situations where the serum albumin is below 2.5 g/dL.

The potential for developing CLS will be evaluated prior to each dose within a cycle by monitoring the subject's weight, orthostatic BP, and pulse. If any subject experiences an increase in weight of 5.5 lb (2.5 kg) or 5% (whichever is greater) of the Day 1 weight of that cycle, or orthostatic BP and pulse changes which are deemed clinically significant, the subject will be thoroughly evaluated for incipient CLS prior to administration of the next dose. Evaluation will include careful physical examination and evaluation of laboratory parameters, including serum albumin, which may indicate CLS.

#### **5.2.2.5 Hemolytic Uremic Syndrome**

Any subject with suspected Grade 1-4 HUS will be evaluated as for CLS and in addition will be followed with serial haptoglobin, LDH, CBCs, and urinalyses to detect urine free hemoglobin. Subjects with an unexplained drop in hemoglobin  $\geq 1.5$  g/dL during any treatment cycle should be evaluated for possible HUS. Peripheral blood will be assessed for schistocytes. Patients need not be managed with plasmapheresis, and rather may be managed with fluid repletion and/or diuretics at the discretion of the institution PI, with consultation of the sponsor. If HUS of any grade develops, treatment should be suspended until resolution of all laboratory abnormalities, and should only be resumed if the maximum grade was  $\leq 2$ , and after consultation and agreement with the sponsor. [REDACTED]

[REDACTED] Diuresis early on may worsen the creatinine by causing dehydration, and should only be used to treat symptoms of fluid overload. Patients may have creatinine elevations and/or microscopic hematuria without evidence of HUS, but such patients may be managed similarly with attention to adequate hydration. Patients should be observed carefully for evidence of severe HUS, including mental status abnormalities, renal failure, and bleeding from severe thrombocytopenia.

#### **5.2.2.6 Ocular Events**

In the event of visual symptoms of Grade 2 or greater, an ophthalmologic evaluation is required. Subjects must be queried for and encouraged to report any ocular symptoms on dosing days prior to the administration of moxetumomab. [REDACTED]

[REDACTED] Due to the potential association of HUS with retinal damage, subjects with visual symptoms and new finding(s) on ophthalmologic examination should be

hospitalized with daily monitoring of renal function with serum creatinine and close observation.

If the subject displays any retinal abnormalities, dosing with the investigational agent must be discontinued. In the event that an ocular event or symptom occurs without any evidence of retinal abnormalities, dosing must be interrupted and may not resume until there is full resolution of ocular symptoms.

### 5.3 Duration of Therapy

Treatment may continue until one of the following criteria applies:

- Completion of 6 cycles of therapy.
- Disease progression
- Documented CR without assessable MRD
- Treatment delay of > 2 weeks beyond scheduled start of subsequent cycle
- Intercurrent illness that prevents further administration of treatment
- Unacceptable AEs as defined in Section 6
- General or specific changes in the patient's condition render the patient unacceptable for further treatment in the judgment of the investigator.
- Severe or life-threatening anaphylaxis or hypersensitivity reaction
- Withdrawal of consent from further treatment with investigational product or lost to follow-up
- Subject is determined to have met one or more of the exclusion criteria or failed to meet all of the inclusion criteria for study participation
- Pregnancy
- Any of the following liver function abnormalities:
  - ALT or AST > 5 x ULN for more than 2 weeks
  - ALT or AST > 3 x ULN and (total bilirubin > 2 x ULN or INR > 1.5); see Section 7.6.2 for additional details regarding reporting of subjects with ALT or AST > 3 x ULN and total bilirubin > 2 x ULN with unknown etiology (ie, Hy's law cases)
  - ALT or AST > 3 x ULN with the appearance of fatigue, nausea, vomiting, right upper quadrant pain or tenderness, fever, rash, and/or eosinophilia (> 5%)
  - Corrected QT interval (Fridericia) > 500 msec confirmed (persistent for at least 5 minutes; based on manual over-read by medically qualified person) and determined post dose either during continuous 12-lead ECG monitoring or on a repeat 12-lead ECG

Subjects who are permanently discontinued from receiving investigational product will be followed for protocol-specified assessments (Table 10-2) including follow-up of any AEs unless consent is withdrawn specifically from further study participation, the subject is lost to follow-up, the subject starts alternative treatment, or the subject is enrolled in another clinical study.

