### 3 PATIENT SELECTION

#### 3.1 Eligibility Criteria

##### 3.1.1 Inclusion Criteria

1. Patients must have histologically confirmed HCL or HCL variant with a need for therapy based on at least one of the following criteria:
  - a. neutrophils  $< 1.0 \times 10^9/L$
  - b. platelets  $< 100 \times 10^9/L$
  - c. hemoglobin  $< 10 \text{ g/dL}$
  - d. symptomatic splenomegaly
2. Patients must be Pseudomonas-immunotoxin naïve
3. Patients must have received at least 2 prior systemic therapies, including 2 courses of courses of a PNA, or 1 course of either rituximab or BRAF inhibitor following a single prior course of PNA.
4. Men or women age  $\geq 18$  years. Because this disease does not generally occur in children, children are excluded from this study.
5. Eastern Cooperative Oncology Group (ECOG) performance status  $\leq 2$  ([Appendix 2](#)).
6. Patients must have adequate organ function as defined below:
  - a. total bilirubin  $\leq 1.5 \text{ mg/dL}$ , unless consistent with Gilbert's (ratio between total and direct bilirubin  $> 5$ )
  - b. AST and ALT  $\leq 3 \times$  upper limit of normal (ULN)
  - c. alkaline phosphatase  $\leq 2.5 \text{ ULN}$
  - d. serum creatinine  $\leq 1.5 \text{ mg/dL}$  or creatinine clearance  $\geq 60 \text{ mL/min}$  as estimated by the Cockcroft-Gault equation ([Appendix 3](#))
7. Prothrombin time (PT)/international normalized ratio (INR) or partial thromboplastin time (PTT)  $< 2.5 \text{ ULN}$ , fibrinogen  $\geq 0.5$  lower limit of normal; if on warfarin, INR  $< 3.5$ , if on any other anticoagulation, PT  $< 2.5 \times$  baseline
8. Ability to understand and the willingness to sign a written informed consent document.
9. Life expectancy  $\geq 6$  months.
10. Females of childbearing potential who are sexually active with a nonsterilized male partner must use a highly effective method of contraception prior to study entry and or the duration of study participation, and must agree to continue using such precautions for 4 months after completion of moxetumomab pasudotox administration; cessation of

contraception after this point should be discussed with a responsible physician. Periodic abstinence, the rhythm method, and the withdrawal method are not acceptable methods of contraception.

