## 6 DOSING DELAYS/DOSE MODIFICATIONS

- There will be no dose reductions for moxetumomab pasudotox.
- Dosing may be delayed up to 2 weeks for toxicity or logistical reasons. Patients should not begin a subsequent treatment cycle of moxetumomab if there is active, ongoing infection requiring treatment. Patients with excessive delay (delay > 2 weeks) are permanently discontinued from treatment and should be followed but not retreated.
- Moxetumomab pasudotox infusion should be interrupted for Grade 2 or Grade 3 infusion related reactions (eg, rapid tumor lysis) and should be permanently discontinued for Grade 4 (life-threatening) anaphylaxis or hypersensitivity reaction
- Patients with  $\geq$  Grade 3 CLS or  $\geq$  Grade 3 HUS should be permanently discontinued from treatment.
- If the ANC is  $< 1.0 \times 10^9/L$ , dosing should be held during Grade 1 or higher fever ( $\geq 38.0^\circ C$ ).
- Dosing should be delayed until Grade 3 or Grade 4 AEs attributed to the study drug decrease to at least Grade 2 or below EXCEPT for the following (ie, dosing delay not required if any of the following are present):
  - Grade 3 hematologic toxicity.
  - Grade 4 hematologic toxicity resolving within < 4 weeks (lymphopenia, leukopenia and lymphocyte subsets will not be considered as grounds for a dosing delay).
  - Hematologic toxicity managed with transfusion and/or other support.
  - Grade 3 transaminase elevations.
  - Grade 3 electrolyte and mineral levels, hyperlipidemia, lipase, proteinuria and fever not associated with  $ANC < 1.0 \times 10^9/L$ .

- Hypocalcemia is graded after correction for the albumin, which increases the measured calcium level by 0.2 mmol/L or 0.8 mg/dL for each 1 g/dL of albumin less than 4 g/dL.
- An event of  $\geq$  Grade 2 hypercalcemia with calcium level corrected for serum albumin will require a delay in dosing until resolution to  $<$  Grade 2.
- Worsening of the coagulation profile of patients on anticoagulation.
- Grade 4 hyperlipidemia if pre-existing at Grade 2-4 levels or resolved to  $<$  Grade 4 by  $<$  2 months.
- Grade 3 hypoalbuminemia unless related to CLS.
- After dosing delays and re-challenge:
  - Patients who redevelop  $\geq$  Grade 3 non-hematologic toxicities, which are not covered by the exclusions in this section, with at least possible attribution to the study drug, will result in the patient discontinuing treatment but not off-study.

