### 7.6.2 Hepatic Function Abnormality

AEs of hepatic function abnormality of special interest to the sponsor are defined as any increase in ALT or AST to greater than  $3 \times \text{ULN}$  **and concurrent** increase in bilirubin to greater than  $2 \times \text{ULN}$  (ie, Hy's law cases). Concurrent findings are those that derive from a single blood draw or from separate blood draws taken within 8 days of each other. In the event of hepatic function abnormality where the etiology is unknown, timely follow-up investigations and inquiries should be initiated by the investigational site, based on medical judgment, to make an informed decision regarding the etiology of the event.

If the underlying diagnosis for the hepatic function abnormality is known (including progression of pre-existing disease such as primary or metastatic malignancy), the diagnosis should be recorded as an AE/SAE.

If the underlying diagnosis for the hepatic function abnormality remains unknown, the term "hepatic function abnormal" should be used to report the AE/SAE.

[REDACTED]

The investigator will review the data with the medical monitor. The investigator should then use clinical judgment to establish the cause based on local standard of care and follow the subject by conducting testing as clinically indicated.

- If, after appropriate workup, in the opinion of the investigator, the underlying diagnosis for the abnormality remains unexplained, or is considered attributable to investigational product, permanent discontinuation of dosing for the study subject should be considered.

Each reported event of hepatic function abnormality will be followed by the investigator and evaluated by the sponsor.

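### Protocol Section 5.3 ends treatment for ALT/AST > 3 x ULN with bilirubin > 2 x ULN whatever the cause, while Section 7.6.2 only asks that a stop be considered; the INR alternative in 5.3 makes no provision for anticoagulated patients.

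*Protocol*

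**What the plan says.** **Section 5.3 (Duration of Therapy)** opens with "Treatment may continue until one of the following criteria applies". Its liver items include "ALT or AST > 3 x ULN and (total bilirubin > 2 x ULN or INR > 1.5"). None of the liver items carries a condition on cause or leaves the decision to the investigator. Section 5.3 refers to Section 7.6.2, but only for details of reporting.

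**Section 7.6.2 (Hepatic Function Abnormality)** defines an event of special interest by ALT or AST above 3 x ULN with a concurrent bilirubin above 2 x ULN. If the workup leaves the event unexplained, or the investigator attributes it to the product, then "permanent discontinuation of dosing for the study subject should be considered". If a cause is known, the visible text says how to record the diagnosis and attaches no stop.

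**Section 3.1.1 (Inclusion Criteria)** caps AST and ALT at 3 x ULN in item 6b. Item 7 gives a separate limit for one group of anticoagulated patients: "if on warfarin, INR" below 3.5.

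**Section 6 (Dosing Delays/Dose Modifications)** lists events that need no dosing delay. Among them are "Grade 3 transaminase elevations" and "Worsening of the coagulation profile of patients on anticoagulation". It does not mention the liver criteria of 5.3.

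**The concern.** A site managing a patient with raised transaminases and bilirubin has two sections to consult. One ends treatment. The other, which is the section devoted to this event, makes ending treatment something to weigh after a workup. The combination is the protocol's own marker of possible drug-induced liver injury, so the consequence should not depend on which page is open.

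The INR alternative raises a different question. Alongside a transaminase rise, a raised INR normally serves as a sign of impaired liver function. In a warfarin patient it may reflect only the anticoagulant. Eligibility expressly allows such patients, and Section 6 tolerates their coagulation changes, yet 5.3 treats their INR like anyone else's.

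At stake are consistent handling of a hepatic safety signal across sites and the meaning of any tabulated discontinuations for liver events.

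**Working it through.** The protocol states no figure on this point, so there is none to reproduce. The check sets the rules side by side and applies their printed thresholds to illustrative patients.

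**Rules as printed**

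- 5.3 stop: (ALT/AST > 5 x ULN for more than 2 weeks), or (ALT/AST > 3 x ULN and [bilirubin > 2 x ULN or INR > 1.5]), or (ALT/AST > 3 x ULN with listed symptoms).
- 7.6.2 event: ALT/AST > 3 x ULN and bilirubin > 2 x ULN. Consequence: a stop is to be considered, if unexplained or attributed to the product.
- Entry limits: ALT/AST at most 3 x ULN; INR below 3.5 on warfarin.

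**Illustrative patients** (values assumed; no symptoms; bilirubin and INR unremarkable unless given)

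| Patient | 5.3 | 7.6.2 |
|---|---|---|
| ALT 4 x, bilirubin 2.5 x | stop | event; stop to be considered |
| ALT 8 x, bilirubin 2.5 x | stop | event; stop to be considered |
| Warfarin, INR 2.5, ALT 2.9 x | no stop | no event |
| Warfarin, INR 2.5, ALT 3.1 x | stop | no event |
| No anticoagulant, INR 1.0, ALT 3.1 x | no stop | no event |
| ALT 8 x alone, 1 week | no stop | no event |
| ALT 8 x alone, 3 weeks | stop (duration) | no event |

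**Bilirubin combination (rows 1 and 2).** The thresholds are the same in both sections; the consequences differ. In 5.3 the stop does not depend on cause. In 7.6.2 even a drug-attributed case leads only to consideration, and a case with a known cause leads to no stop in the visible text.

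**INR alternative (rows 3 to 5).** Rows 4 and 5 share the same ALT and differ only in INR. The INR of 2.5 in row 4 is one that inclusion criterion 7 accepts in a warfarin patient. The range both eligible on warfarin and above the 5.3 cut-off runs from 1.5 to 3.5. Inside it the INR half is already met, and the criterion becomes ALT/AST > 3 x ULN alone. Row 3 shows that INR by itself never triggers the stop. Because item 6b caps entry at 3 x ULN, nobody eligible meets the combined criterion at entry.

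**Section 6 (last two rows).** Its exemption names transaminase elevations of Grade 3 only. ALT of 8 x for 1 week meets no 5.3 stop, so nothing conflicts. At 3 weeks 5.3 stops on duration. If the value is Grade 3, Section 6 merely does not require a delay, which is a different action. The protocol prints no numerical Grade 3 boundary for ALT/AST, so the exact overlap cannot be fixed from it.

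**The case against.** The strongest defence is that 5.3 governs how long treatment lasts, while 7.6.2 stands under events requiring immediate reporting. A site that stops under 5.3 has also satisfied an instruction to consider stopping, so both can be obeyed, and redosing would mean ignoring an explicit criterion. Part of 7.6.2 is blacked out and may say more. It is true that the two can be obeyed together. But 7.6.2 addresses dosing directly, and its visible sentence offers a discretion that 5.3 does not give. That mismatch remains whatever the hidden text says.

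On INR, the missing exception may be deliberate caution, and no section forbids it. That is fair. It makes this a gap to be clarified, not a contradiction. It concerns only patients whose INR exceeds 1.5 and whose ALT/AST then passes 3 x ULN.

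Three stronger readings are tempting and are not supported:

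- **That Section 6 exempts the same abnormality.** It lists neither bilirubin, nor the combined picture, nor the transaminase-plus-INR criterion. Its main effect is on delay, and 5.3 lists its liver stops separately from adverse events defined in Section 6. One link deserves clarification: the last bullet of Section 6 uses the same exclusions to limit a permanent stop after re-challenge, without mentioning the 5.3 liver criteria.
- **That Section 5.1.1 contradicts the symptom criterion in 5.3.** Section 5.1.1 allows secondary premedication for "infusion-related reactions, including, but not limited to pyrexia, nausea, or dyspnea" and says nothing about transaminases. The 5.3 criterion, "ALT or AST > 3 x ULN with the appearance of fatigue, nausea, vomiting" and other listed findings, needs both elements together.
- **That each stopped patient costs the primary rate 1/77 = 1.3 percentage points.** Stopped patients remain in protocol assessments (5.3), have the end-of-treatment marrow and imaging (3.3.4.1) and stay in the intent-to-treat population (13.2). An early stop is therefore not automatically a lost response.

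**Conclusion.** The point holds for the bilirubin combination: 5.3 and 7.6.2 attach different consequences to the same transaminase and bilirubin thresholds, and the cross-reference between them covers reporting only. This is a contradiction in a safety rule, visible in unredacted text, and it needs no assumption about grading cut-offs.

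It holds in smaller form for INR: for a warfarin patient with INR between 1.5 and 3.5, the two-part criterion works as a one-part criterion once ALT/AST exceeds 3 x ULN.

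The number of patients affected is unknown, and the documents give no basis for estimating it. Differences between sites are a possibility that the wording creates, not something shown to have occurred. No view is taken on which clinical rule is right.

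**What to change.** - Reconcile Sections 5.3 and 7.6.2 so that both state the same consequence for ALT/AST > 3 x ULN with bilirubin > 2 x ULN, including whether cause matters.
- State in 5.3 how the INR part applies to patients whose INR is raised by permitted anticoagulation.
- Add a cross-reference in Section 6 saying how its Grade 3 transaminase exemption relates to the 5.3 liver criteria, both for delay and for the re-challenge bullet.

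The sponsor's clinical and safety teams decide which rule stands. The cost is a wording amendment to three sections and a notice to sites; no new procedure, visit or sample is needed.
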